- Individuals engaged in the research will not have any part in any decisions as to the timing, method, or procedures used to terminate a pregnancy.
- Individuals engaged in the research will not have any part in determining the viability of a neonate.

Section J: Consent Process – Consent Required

J1. Describe when the consent process will take place with the potential participant.

Participants should be approached prior to the initiation of any study procedures and should not be approached in a situation where they may feel compromised (e.g. while in labour, just prior to a surgical procedure or under sedation).

This study will be advertised on study brochures placed in the antenatal clinics/wards and preoperative rooms/wards. They will be given to all parturients who meet the inclusion criteria during the antenatal period. On admission to preoperative rooms/wards, they will again be given a study brochure if the patients have pain score of 3 or less (out of 10 using numerical rating scale) and not in distress. The investigators and study team will be available to answer any queries on this trial in the antenatal clinics/wards and preoperative rooms/wards. With the activation of HBRA, informed consent will be obtained in the presence of a prescribed witness.

Recruitment of patients from antenatal clinics/wards:

All potential patients who are expected to meet the inclusion/exclusion criteria at term are seen in the KKH antenatal clinics/wards will be invited to participate in the study. The informed consent process may be conducted at any time during prior to labour. However, the patient will not be enrolled in the study until they have met all the inclusion criteria and exclusion criteria. If a patient consents prior to labour, a copy of the consent form will be kept in the patient's case notes. The study investigator will recheck the inclusion/exclusion criteria when the patient is at the preoperative rooms/wards prior to the initiation of the study activities. Obstetricians and research team will approach the patients in the antenatal clinics/wards to provide information about the study.

Recruitment of patients at preoperative rooms/wards:

The patients will receive the study brochure when they arrive at the preoperative rooms/wards if the patients have pain score of 3 or less (out of 10 using numerical rating scale) and not in distress.

Screening for inclusion/ exclusion criteria will be performed and discussion of the study will be done by the study investigators.

All patients who choose to enrol in the study will be counselled by the investigators about the study protocol, both verbally and with the patient information sheet. Adequate time will be given for discussion and with the investigators to clarify any doubts. The risks and benefits in joining this study will be clarified at recruitment prior to written consent.

J2. Where will the consent process take place with the potential participant (e.g. in room ward, outpatient clinic etc.)? Please justify why the place chosen for the consent process is suitable.

Informed consent will be taken place in the antental clinic/wards and preoperative rooms/wards in a private manner.

J3. Please describe the consent process as follows:

i. Explain if adequate time will be given to the participant to consider their participation.

This study will be advertised on study brochures placed in the antenatal clinics/wards and preoperative wards/rooms. They will be given to all parturients who meet the inclusion criteria during the antenatal period. The patients will receive the study brochure again when they arrive at the preoperative wards/rooms if the patients have pain score of 3 or less (out of 10 using numerical rating scale) and not in distress. Investigators or Clinical Research Coordinators will explain to the patients about the study and patients will be given ample time to read the informed consent form about the study before obtaining their consent.

ii. Please explain if the place where consent will be taken is suitable. This place should allow the participants to be comfortable and have the right frame of mind to consider participation.

Participants will be approached in the antenatal clinic/wards and preoperative rooms/wards. The discussion will be conducted in private manner with the patient.

iii. Please explain how the person taking consent would minimise the possibility of coercion or undue influence.

Participants will receive a patient information sheet. This will be discussed with them in private manner in the antenatal clinic/wards and preoperative rooms/wards. The subjects are able to withdraw from the study at any point. The contact details of the Principal Investigator will be provided in the information sheet. Patients are free to withdraw the study at any time (including timing after their delivery), should they decide not to participate.

J4. Does your study involve potential vulnerable participants whereby obtaining informed consent from the participant is not possible and informed consent is required from a Legal Representative (LR)? No

J5. Please describe the provisions to protect the "privacy interest" of the participants (e.g. consent will be obtained in a separate room, free from intrusion and participants are comfortable with the proposed settings).

Research personnel will conduct all the discussions about the study and answer any question in private manner.

J6. Will consent be documented in the form of a written and signed Research Participant Information Sheet and Consent Form?

Yes

File Name	Description	Version Number	Version Date
EPOC PIS Version 5 (tracked changes).doc	EPOC PIS (tracked changes)	5	24May2018
EPOC PIS Version 5 (clean copy).doc	EPOC PIS (clean copy)	5	24May2018

J7. Will research participants receive any monetary payments (including transportation allowances) or gifts for their participation in the study?

Yes

Participants will be reimbursed SGD20 for their time, inconvenience & transportation.

J8. Besides the Informed Consent Form, will any other materials or documents be used to explain the study to potential Research Participants (e.g. scripts, hand outs, brochures, videos, logs etc.)?

No

J9. Will the study enrol non-English speaking participants?

No

J10. Will the study be recruiting under emergency situations, when prior consent of participant is not possible, and the consent of the participant's legal representative, if present, should be requested?

No

J11. Do you have any additional comments regarding the Informed Consent process?

No

Section K: Research Data Confidentiality

K1. Will coded/anonymous research data be sent to the study sponsor (e.g. pharmaceutical sponsored studies)?

No, the study team would store all research data within the institution.

i. Please state where the research data (soft copy and/or hardcopy) will be stored and indicate if the location storage is secured (i.e Password Protected PC or Laptop, data stored in physical location with lock and key access.)

The soft copy of research data will be stored in a password protected PC. Hard copies of data collection forms are kept by the Principal Investigator under lock and key. The data is accessible only by Investigators for analysis purposes only.

Our recruited subjects/ participants can also do online survey (on Survey Monkey platform) 6-10 weeks follow up instead of only phone survey. The online survey data will be stored in Survey

Monkey's data center with reliable power sources and backup systems. Physical security controls are also ensured in their data center. The data will be encrypted using secure TLS cryptographic protocols. Participants' confidentiality will be protected as the online survey link will be sent to their email address only. No names or identification number that will identify subjects will be available on the online surveys and in the system. The survey data will then be extracted from the online system as password protected excel file. The soft copy of research data will be stored in a password protected

PC. The data is accessible only by Investigators for analysis purposes only.

ii. Who will have access to the research data, and how will access to the research data be controlled and monitored? (Please state the personnel who will have access to the study data eg.

Principal Investigator, Co-Investigator, study coordinator.)

An electronic database REDCap will be used for data entry into case report form (CRF). Password protected accounts will be created for relevant study personnel and the degree of database access granted to the each relevant study personnel (Principal Investigator, Co-Investigator and Clinical Research Coordinator) account will correspond to their trial responsibilities. The research data will be locked and soft copy will be under the computer security of Singhealth.

For the 6-10 weeks online survey, participants' confidentiality will be protected as the online survey link will be sent to their email address only. No names or identification number that will identify subjects will be available on the online surveys and in the system. Only the Principal Investigator and designated Clinical Research Coordinator will have the access to the online surveys by using the designated secured password protected survey monkey login account.

iii. Are there any other measures in place to protect the confidentiality of the research data?

For electronic database REDCap, No names or identification number that will identify subjects will be ensured. The subjects are only identified by study number.

For online survey, No names or identification number that will identify subjects will be available on the online survey and in the system.

iv. Are there any research data sharing agreements with individuals or entities outside the Institution, to release and share research data collected?

No

v. Describe what will happen to the research data when the study is completed.

The research data will be kept under lock and key and using computer security of Singhealth. The data will be destroyed after keeping for 6 years upon completion of the study.

K2. Will any part of the study procedures be recorded on audiotape, film/video, or other electronic medium?

No

Section L: Data & Safety Monitoring

L1. The purpose of the Data and Safety Monitoring Plan is to ensure the safety and well-being of participants, and the integrity of the data collected for the study. Depending on the type and risk level of the study, this may include the Principal Investigator, experts within the department or institution, independent consultants or a combination of the said persons.

Who will perform the data and safety monitoring?

The data is kept by the principal investigator under lock and key and using computer security of SingHealth. The data is accessible only by the investigators for analysis purposes only. The plan for adverse effect monitoring would include reporting to Health Science Authority and CIRB.

L2. Please describe the frequency of review (e.g. daily, weekly, quarterly) and what data (e.g. adverse events/serious adverse events) will be monitored for safety.

Safety data is monitored at all times by the investigators. There will be monthly meeting to review the trial.

Adverse events and serious adverse events will be reported to CIRB accordingly.

L3. How is data integrity monitored to ensure that study data is authentic, accurate and complete, and if the data correlates with the case report forms?

Data is extracted from data collection forms and random audits will be performed to make sure it is authentic, accurate and complete.

L4. Please describe the stopping criteria for the research study based on efficacy, futility and safety criteria.

The stopping criteria for the research study will be based on safety criteria. The review of serious adverse effects will be performed.

L5. Please state the route of dissemination of any data and safety information to the study sites, as well as the person/team responsible for doing so.

Face-to-face communication and email correspondence.

Other Attachments

Note: Please attach only documents that are not relevant to the above sections.

File Name	Description	Version Number	Version Date
EPOC PDPA.pdf	EPOC PDPA	1	-

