E4. Who will be responsible for research-related costs? For sponsored studies, please list the costs that will be borne by the sponsor.

Anaesthesiology ACP Pilot Research Grant

Section F: Research Methodology

F1. Please provide an abstract of your proposed research (Up to 300 words).

Approximately 1 in 5 women who undergo cesarean delivery would suffer from severe post-operative pain, which may further increase their risks from developing postpartum depression. Predictive factors such as pre-operative pain, age and anxiety could significantly contribute to post-operative nausea and vomiting (PONV) and pain in general surgery, however little information is available with regards to cesarean delivery. Previous studies demonstrated that pain scores upon local anesthetic injection is positively correlated to post-cesarean pain scores. Additionally, anxiety, anticipated post-operative pain score and anticipated medication need are also found to be promising risk factors to postcesarean pain management.

We aim to investigate the risk factors of causing post-operative emesis after cesarean delivery, and to reaffirm that there is a positive correlation between pain on local anesthetic injection, presence of mechanical temporal summation (MTS) and post-Cesarean pain scores. We will recruit 200 parturients undergoing cesarean delivery at KK Women's and Children's Hospital and requiring regional anesthesia. Pain and anxiety assessment will be conducted via visual analogue scoring (VAS), MTS assessment and a series of questionnaires. After the delivery, all patients will be given appropriate analgesia, and the pain score at movement will be recorded. Secondary outcomes include pain scores at rest, analgesia consumption, time-to-first-rescue analgesia, opioid-related side effects, patient satisfaction and postpartum depression.

This proposal will determine the clinical relevance of pre-operative determinants for post-cesarean pain management in local context. This would help us discover new risk management strategies and identify modifiable treatment. We hope that this will serve as a guideline for consistent and reliable delivery of care while enhancing the effectiveness and patient satisfaction in obstetrics pain management.

F2. What are the specific aims and hypothesis of this study?

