Our prospective group study will investigate the role of modifiable risk factors and develop a model that would take into account biological and psychological mechanisms to better understand PONV and pain after cesarean surgery. We will identify modifiable risk factors and explore the interplay of psychological and pain pathways will be investigated through targeted selected serotonin, monoamine and oxytocin candidate gene polymorphism with post-operative pain, PONV and postnatal depression. Our study will broaden the current understanding and basic neurobiological mechanisms especially in central sensitisation and central nervous system dysregulation in PONV and post-operative pain. We will validate the role of analgesic interventions and needs in reducing the risk of PONV and post-cesarean pain and change the current clinical practice in the care during cesarean delivery management. The proposed study will guide us in future studies on potential novel risk stratification and identify modifiable risk factors as therapeutic targets.

F7. Long Term Implications of Research

The long term goal of our project is to establish a collaborative care model according to each individual's risk factors and eventually to target specified interventions to minimize the risk of PONV and improve the pain experience after childbirth. The psychobiological model derived from this trial could be the basis of subsequent hypothesis testing in research into modifiable risk factors, as well as, validation of the model in a new population group such as other pain syndromes. This trial would aim to develop prediction and model validation in the long term. We plan to incorporate a longer term follow-up study (2 to 3 years) following this proposal to examine the sustained effect of these risk factors on post-operative pain and depression after childbirth including health sciences outcomes like cost-effectiveness analysis and longer term functional outcomes.

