Patients will be asked to rate, using a 0-10mm visual analog scale (VAS), their surgical anxiety level ("On a scale of 0-100, with 0 being not anxious at all to 100 being extremely anxious, how anxious are you about your upcoming surgery?"), their anticipated pain (On a scale of 0-100, with 0 being no pain at all and 100 being pain as bad as you can imagine, how much pain do you anticipate experiencing after your upcoming surgery?"), and using a categorical scale, their anticipated pain medication need ("On a scale of 0 to 5, with 0 being none at all, 1 being much less than average, 2 being less than average, 3 being average, 4 being more than average, and 5 being much more than average, how much pain medication do you anticipate needing after your upcoming surgery?").

Study survey will be administered upon recruitment in antenatal clinic or delivery suite or till 5-14 days after discharge whenever patient is comfortable. It includes Edinburgh Postnatal Depression Scale (EPDS), Pain Catastrophizing Scale (PCS), Central Sensitisation Inventory (CSI), EQ-5D-3L and HADS. The estimated duration of the surveys is about 30 minutes.

Mechanical temporal summation (MTS) assessment using a 180 gram von Frey filament applied to the patient's arm, as demonstrated by Weissman-Fogel, et al.[20], will be done prior to surgery and results recorded. The anesthetic technique will be standardized using the current standards of care. All women will receive antacid prophylaxis with 30 ml sodium citrate. The spinal anesthesia administered will be standardized doses of intrathecal hyperbaric bupivacaine (10.5-12 mg), fentanyl (15 mcg), and preservative-free morphine (100 mcg). Before placing the spinal anesthetic, the skin at the site will be infiltrated with 2-5 ml 1.0% lidocaine as per standard practice. It has been shown that the words used during local anesthetic injection can influence patient's subjective experience of pain, so prior to local anesthetic injection we will use a standardized script to inform patients that local anesthetic is about to be given: "I am now giving you the numbing dose." After the injection is completed and the needle is removed, the anesthesiologist will use a standardized script, "From 0 to 10, where 0 is no pain and 10 is the worst pain imaginable, how much did this procedure hurt?" Patient's responses will be recorded.

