During cesarean delivery: Surgery, intraoperative and postoperative management will be performed according to standard practice. Data will be collected on heart rate, blood pressure, oxygen saturation, presence of nausea and vomiting and use of wound infiltration. Acute pain in the postoperative care unit (PACU) will be treated at clinician's discretion.

After delivery and before discharge from the hospital: The woman is interviewed at 0 to 48 hours on the pain scores at rest and with movement (sitting up in bed from a supine position) and will be recorded in the nursing electronic records. Other data such as nausea scores, and occurrence of vomiting are also noted. Standard routine monitoring of haemodynamics parameters and pain relief will be done in the ward. Study surveys are continued while patient is comfortable before discharge or till 5-14 days after discharge. The survey for post-delivery health status (HADS, EQ-5D-3L) will take about 10 minutes to complete.

Six - Ten weeks after delivery: The patient will have a phone survey/ online survey at 6 -10 weeks post-delivery with: (1) EPDS (2) Pain Survey (3) Pain Vulnerability (PCS, CSI) (4) Breastfeeding Questionnaire (5) EQ-5D-3L and (6) HADS. Patients with scores on the depression scale consistent with postpartum depression will be referred to their obstetrician or primary care physician for further assessment and management.

F9. Please provide details on sample size and power calculation and the means by which data will be analyzed and interpreted (if applicable).

As an observational study, we will target to enrol for up to 200 consented subjects. The primary hypothesis will be assessed with a Pearson correlation test at $\alpha=0.05$ cutoff for statistical significance. The secondary numeric measures of pain, nausea, and satisfaction will be assessed for correlation with the preoperative measures using a Pearson correlation test. Anticipating that some patients will not require rescue oxycodone, we plan to analyze the time to rescue oxycodone via Kaplan-Meier mean time to event analysis. Dichotomous variables will be assessed via chi-square tests or fisher exact tests.

F10. List all activities that are carried out as part of research in this study. Please state/list all procedures involved in this research study and attach the data collection form (if any) which will be used for CIRB review.

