The duration of study period for each participant can last about 17 weeks. Below are the main time points for the study activities:

Before surgery (duration: 4 weeks):

- Patient screening and recruitment before the surgery: gestational age week 36 and above
- Baseline Demographic data collection
- Survey and data collection (EPDS, pain score, vital signs, HADS score, EQ-5D-3L, MTS, "three questions", pain vulnerability (PCS, CSI))

After surgery (duration of labour till 5-14 days after discharge: ~19 days):

- Pain assessment, survey and data collection (pain score, vital signs, HADS score, EQ-5D-3L, analgesia usage, occurrence of vomiting, and nausea scores)

Follow up phone call survey at 6 - 10 weeks after delivery (duration: 10 weeks):

- Phone survey/ Online survey and data collection (EPDS, breastfeeding, HADS score, EQ-5D-3L, pain score, and pain vulnerability (PCS, CSI))

F11. Please describe the participant's visits (frequency and procedures involved). For studies with multiple visits, please attach study schedule.

There will be 3 visits in total. The duration of study period for each participant can last about 17 weeks. Below are the main time points for the study activities:

Visit 1-Before surgery (duration: 4 weeks):

- Patient screening and recruitment before the surgery: gestational age week 36 and above
- Baseline Demographic data collection
- Survey and data collection (EPDS, pain score, vital signs, HADS score, EQ-5D-3L, MTS, "three questions", pain vulnerability (PCS, CSI))

Visit 2-After surgery (duration of labour till 5-14 days after discharge: ~19 days):

- Pain assessment, survey and data collection (pain score, vital signs, HADS score, EQ-5D-3L, analgesia usage, occurrence of vomiting, and nausea scores)

Visit 3-Follow up phone call survey at 6 - 10 weeks after delivery (duration: 10 weeks):

- Phone survey/ Online survey and data collection (EPDS, breastfeeding, HADS score, EQ-5D-3L, pain score, and pain vulnerability (PCS, CSI))

F12. Discuss the potential difficulties and limitations of the proposed procedures and alternative approaches to achieve the aims.

There will be drop out in the follow up phone survey. However, the withdrawal rate has been accounted for.

F13. What are the potential risks to participants?

During the MTS pain assessment, a test would involve the repeated sensation of pinprick testing for increased sensitivity of pain to pinprick in some individuals.

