All potential patients who are expected to meet the inclusion/exclusion criteria at term and are seen in the KKH antenatal clinics/wards will be invited to participate in the study.

The informed consent process may be conducted at any time during prior to labour. Obstetricians and research team will approach the patients in the antenatal clinics/wards to provide information about the study. If a patient consents prior to labour, a copy of the consent form will be kept in the patient's case notes. The study investigator will recheck the inclusion/exclusion criteria when the patient is at the preoperative rooms/wards prior to the initiation of the study activities.

Recruitment of patients at preoperative rooms/wards:

The patients will receive the study brochure when they arrive at the preoperative rooms/wards if the patients have pain score of 3 or less (out of 10 using numerical rating scale) and not in distress. Screening for inclusion/ exclusion criteria will be performed and discussion of the study will be done by the study investigators.

G4. Will any advertising/recruitment materials be used to recruit research participants?

Yes

Brochures

Please state the location(s) where the brochures will be placed (e.g. in the general waiting area in Clinic X), and attach a copy of the brochure.

Brochures will be placed and distributed in Antenatal clinics/wards and preoperative

G5. Will any other recruitment strategies be used (e.g. talks in public places, societies etc.)? No

G6. What is the Recruitment Period (if applicable)? Please provide us with the approximate recruitment period.

Start Date: 01-Jun-2017

End Date: 01-Jun-2019

G7. How long will the participants be directly involved in the study (if applicable)? This includes the time from the screening procedures till completion of follow-up tests or examinations.

If applicable, please elaborate.

The duration of study period for each participant can last about 17 weeks. Below are the main time points for the study activities:

- Screening and recruitment time point: gestational age week 36 and above (duration: 4 weeks)
- Pain assessment and questionnaire completion time point (duration of labour till 5-14 days after discharge: ~19 days)
- Follow up phone call survey time point: 6-10 weeks after delivery (duration: 10 weeks)

Section H: Study Sites & Recruitment Targets

H1. Please state the target number of research participants to be recruited for each study site.

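### F8 allows the pre-delivery questionnaires to be completed up to 5-14 days after discharge, after the 0-48 h pain outcome, while F10 and F11 list them as before-surgery data

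*Protocol*

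**What the plan says.** Protocol F8, in the part on procedures before delivery, sets this window: "Study survey will be administered upon recruitment in antenatal clinic or delivery suite or till 5-14 days after discharge whenever patient is comfortable". The sentence that follows defines the survey as the EPDS, PCS, CSI, EQ-5D-3L and HADS, and the whole set is put at about 30 minutes.

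F8 repeats the window for the period after delivery: "Study surveys are continued while patient is comfortable before discharge or till 5-14 days after discharge". It then describes a separate, shorter survey: "The survey for post-delivery health status (HADS, EQ-5D-3L) will take about 10 minutes to complete".

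F10, under its before-surgery heading, and F11, under Visit 1, both list "Survey and data collection (EPDS, pain score, vital signs, HADS score, EQ-5D-3L, MTS", followed by the three questions and the PCS and CSI. All five instruments are thus before-surgery data there. The after-surgery list in F10 and F11 contains HADS and EQ-5D-3L but not EPDS, PCS or CSI, which next appear at 6-10 weeks.

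Pain at rest and on movement is recorded at 0 to 48 hours (F8). In F9 the secondary numeric outcomes "will be assessed for correlation with the preoperative measures using a Pearson correlation test".

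**The concern.** A form completed after discharge complies with F8 and breaches F10 and F11. It also follows the pain and nausea records. Three things are then at stake.

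- **Direction of association.** Catastrophizing, central sensitisation and anxiety or depression scores taken after a painful recovery may be raised by that pain. F9 does not name these scales. If late forms are counted among its preoperative measures, or enter the F6 plan to "develop a model that would take into account biological and psychological mechanisms", part of any association may be pain driving the score rather than the score predicting pain.
- **Baseline for depression.** F1 lists among the secondary outcomes "opioid-related side effects, patient satisfaction and postpartum depression". A late completer has no EPDS from before delivery to show whether symptoms were already present.
- **Visit identity.** HADS and EQ-5D-3L are due at both Visit 1 and Visit 2. If Visit 1 is completed late, both sets may come from the same occasion.

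**Working it through.** **1. Do the stated durations reproduce, and where does the late window fall?** F10 gives 4 weeks before surgery, about 19 days after surgery and 10 weeks of follow-up: 28 + 19 + 70 = 117 days, and 117/7 = 16.7 weeks. This matches the stated figure of about 17 weeks. The 5-14 day post-discharge window lies inside the 19-day after-surgery period, so it is not preoperative time.

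**2. Does a late form always postdate the pain outcome?** Length of stay is not stated. The 19 days less 14 imply about 5 days, so I take 0 to 5 days as the range. Form time = (stay + 5 to 14 days) × 24 h, compared with the 48 h end of the pain records.

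| Assumed stay | Form completed (h after delivery) | Hours after the 48 h window closes |
|---|---|---|
| 0 days | 120 to 336 | 72 to 288 |
| 5 days | 240 to 456 | 192 to 408 |

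A form completed in the 5-14 day period follows the outcome whatever the stay.

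**3. Which instruments are affected?**

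| Instrument | F8, pre-delivery survey with late window | F10/F11 before surgery | F10/F11 after surgery |
|---|---|---|---|
| EPDS, PCS, CSI | yes | yes | no |
| HADS, EQ-5D-3L | yes | yes | yes |

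For EPDS, PCS and CSI the conflict is direct. For HADS and EQ-5D-3L, a late Visit 1 form cannot be told from a Visit 2 form unless it is dated and labelled.

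**4. How large could the effect be?** The protocol gives neither the share of late forms nor any correlation, so this is an illustration. Let a fraction f of forms be late and have correlation r1 with pain, and let the rest have correlation r0. If late and early forms have equal means and variances, the pooled correlation is r = (1 − f)·r0 + f·r1. The rejection rate at two-sided 0.05 (F9 states 0.05 but not sidedness) is approximately Φ(z − 1.960) + Φ(−z − 1.960), with z = atanh(r)·√(N − 3). For N = 200, √197 = 14.04.

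True preoperative correlation r0 = 0, late r1 = 0.4:

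- f = 0.10: r = 0.04, z = 0.56, rejection about 0.081 + 0.006 = 8.7%. Simulation with 40,000 replicates gives 8.8%.
- f = 0.25: r = 0.10, z = 1.41, rejection about 29%. Simulation gives 29.5%.
- f = 0.05: simulation gives 6.1%, close to nominal.

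At f = 0.25, with r1 = 0.2, 0.3 and 0.5, simulation gives 11.0%, 19.0% and 42.7%.

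If the preoperative correlation is real (r0 = 0.2, r1 = 0.4), the pooled value is 0.9 × 0.2 + 0.1 × 0.4 = 0.22 with 10% late and 0.75 × 0.2 + 0.25 × 0.4 = 0.25 with 25% late. These overstate 0.2 by about 10% and 25%.

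**5. What does leaving late forms out cost?** The correlation detectable with 80% power is tanh((1.960 + 0.842)/√(N − 3)): 0.197 for N = 200, 0.208 for N = 180 (10% left out) and 0.227 for N = 150 (25% left out). The loss of precision is small.

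**The case against.** The strongest reply is that F8 loosely describes the whole survey period, and that F10 and F11 settle which instrument belongs to which visit. On that reading the late window concerns only the post-delivery survey. This does not survive the text: the sentence after the window defines the survey as all five instruments, and F8 describes the shorter HADS and EQ-5D-3L survey separately. The late window is also stated twice.

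A second reply is that no stated aim clearly depends on these scales. This largely stands. The primary aim uses injection pain, and secondary aim 1 uses mechanical temporal summation, which F8 places before surgery. The anxiety score in secondary aim 2 is most naturally the VAS item about the coming operation, though HADS is not excluded. F9 names none of the five scales, and F6 states an intention without listing predictors.

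Third, late forms may be rare. F8 permits completion in the antenatal clinic, there are four weeks before surgery, and emergency sections are excluded. But G3 has eligibility rechecked "when the patient is at the preoperative rooms/wards prior to the initiation of the study activities" and also allows recruitment there. A set of about 30 minutes may not fit that slot, and F8 expressly permits deferral. The frequency remains unknown, and at 5% late the distortion is slight.

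Fourth, handling of late forms could be left to the statistical analysis plan. Their exclusion could be. A preoperative score that was never taken could not be restored. It is also fair that EPDS is collected at 6-10 weeks and that no stated analysis adjusts for its baseline. What is lost is the ability to separate new from existing symptoms in late completers.

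**Conclusion.** The concern holds and should be fixed. F8 contradicts F10 and F11 on when five questionnaires are completed, and forms that F8 permits can follow the 0-48 h pain and nausea outcomes. The textual conflict and the timing are certain. The size of any bias is not: it depends on the share of late forms, on how strongly postoperative scores track pain, and on whether late forms are pooled with preoperative ones, none of which the protocol states. Under the assumptions shown, it ranges from negligible at 5% late to serious at 25% late. The damage is confined to the psychological and pain-vulnerability measures, the pre-delivery EPDS, and the separation of Visit 1 from Visit 2 for HADS and EQ-5D-3L. The primary aim is not affected.

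**What to change.** Reconcile F8 with F10 and F11:

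- Require the Visit 1 set (EPDS, PCS, CSI, HADS, EQ-5D-3L) to be completed before the spinal.
- State that it may be completed at the antenatal visit once consent is given, so that the eligibility recheck in G3 does not push it into the preoperative room.
- Keep the window up to 5-14 days after discharge only for the separate post-delivery HADS and EQ-5D-3L.
- Record the completion date and time of every form.
- Label any Visit 1 form completed after surgery as postoperative data, leave it out of predictor analyses, and report how many there were.

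The cost is protocol wording plus a date and time on each form, if these are not already captured. The downside is that some women, especially those recruited in the preoperative rooms, will have no preoperative form. That missingness may be selective, and the small loss of precision does not account for it. Reporting the number makes it visible.
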